2.4 Correlative Studies Background

Additional biomarker research to identify factors important for pembrolizumab therapy will also be pursued. Immune biomarker studies will include immunophenotyping of systemic immune cell subsets, TIL Density and TCR overlap, multi-plex IHC to assess: 1) the proportion of PD-L1 expression on GFAP+ tumor cells versus myeloid cells (CD68+ or CD163+) within the tumor microenvironment, and Gene expression Signatures and somatic mutations in an attempt to develop immune signatures as outlined in Section 8.0.

3. PARTICIPANT SELECTION

Male/female subjects of at least 18 years of age with recurrent glioblastoma who have not received prior bevacizumab, and are candidates for surgical tumor debulking will be enrolled in this trial.

Screening evaluations are detailed in Study Calendar (Section 9). All assessments are to occur within 14 days of registration except where otherwise noted. The participant must be thoroughly informed about all aspects of the study, including the study visit schedule and required evaluations and all regulatory requirements for informed consent. The written informed consent must be obtained from the participant prior to enrollment.

Following registration, any additional laboratory assessments obtained prior to start of treatment will not be used to re-confirm eligibility. Please refer to Section 5.2 Dosing Delays/Dose

Modifications for toxicity management between registration and start of study treatment.

3.1 Eligibility Inclusion Criteria

In order to be eligible for participation in this trial, all subjects must meet the following criteria on screening examination:

- 3.1.1 Have histologically confirmed World Health Organization Grade IV malignant glioma (glioblastoma or gliosarcoma). Participants will be eligible if the original histology was low-grade glioma and a subsequent histological diagnosis of glioblastoma or variants is made.
- 3.1.2 Be willing and able to provide written informed consent/assent for the trial.
- 3.1.3 Be ≥ 18 years of age on day of signing informed consent.
- 3.1.4 Have a Karnofsky performance status (KPS) ≥ 70 (Appendix A).
- 3.1.5 Previous first line therapy with at least radiotherapy.
- 3.1.6 Be at first or second relapse. **Note:** Relapse is defined as progression following initial therapy (i.e., radiation \pm chemotherapy). For participants who had prior therapy for a low-grade glioma, the surgical diagnosis of a high-grade glioma will be considered the first relapse.
- 3.1.7 Participants must have shown unequivocal evidence for tumor progression by MRI or CT scan.
- 3.1.8 Demonstrate adequate organ function as defined in Table 1, all screening labs should be performed within 14 days of registration.

Table 1 Adequate Organ Function Laboratory Values

System	Laboratory Value
Hematological	
Absolute neutrophil count (ANC)	≥ 1.5 K/uL
Platelets	≥ 100 K/uL
Hemoglobin	≥ 9 g/dL or ≥ 5.6 mmol/L without transfusion or EPO dependency (within 7 days of assessment)
Renal	
Serum creatinine OR Measured or calculated ^a creatinine clearance (GFR can also be used in place of creatinine or CrCl)	≤ 1.5 X institutional upper limit of normal (ULN) OR ≥ 60 mL/min for subject with creatinine levels > 1.5 X institutional ULN
Hepatic	

Serum total bilirubin	$\leq 1.5 \times$ institutional ULN OR
	Direct bilirubin \leq institutional ULN for subjects with total bilirubin levels > 1.5 institutional ULN
AST (SGOT) and ALT (SGPT)	$\leq 2.5 \times$ institutional ULN OR $\leq 5 \times$ institutional ULN for subjects with Gilberts syndrome
Albumin	≥ 2.5 mg/dL
Coagulation	
International Normalized Ratio (INR) or Prothrombin Time (PT)	$\leq 1.5 \times$ institutional ULN unless subject is receiving anticoagulant therapy as long as PT or PTT is within therapeutic range of intended use of anticoagulants
Activated Partial Thromboplastin Time (aPTT)	$\leq 1.5 \times$ institutional ULN unless subject is receiving anticoagulant therapy as long as PT or PTT is within therapeutic range of intended use of anticoagulants

^aCreatinine clearance should be calculated per institutional standard.

3.1.9 CT or MRI within 14 days prior of registration.

NOTE: Due to the fact that the screening MRI will not be used for response purposes, participants may be registered if screening CT or MRI is > 14 days of registration if prospective approval is received from Overall PI, [name] (for prospectively approved circumstances an eligibility exception will not need to be filed).

3.1.10 An interval of at least 4 weeks (to registration) between prior surgical resection or one week for stereotactic biopsy.

3.1.11 An interval of at least 12 weeks from the completion of radiation therapy to registration unless there is unequivocal histologic confirmation of tumor progression.

3.1.12 Participants must have recovered to grade 0 or 1 or pre-treatment baseline from clinically significant toxic effects of prior therapy (including but not limited to exceptions of alopecia, laboratory values listed per inclusion criteria, and lymphopenia which is common after therapy with temozolomide).

3.1.13 From registration, the following time periods must have elapsed: 5 half-lives from any investigational agent, 4 weeks from cytotoxic therapy (except 23 days for temozolomide and 6 weeks from nitrosoureas), 6 weeks from antibodies, or 4 weeks (or 5 half-lives, whichever is shorter) from other anti-tumor therapies (including vaccines). No wash-out period required from TTF.

3.1.14 Participants must have sufficient tissue from most recent surgery revealing glioblastoma or variants for submission following registration. The following amount of tissue is required:

- 1 formalin-fixed paraffin-embedded (FFPE) tumor tissue block

3.1.15 Patients with a prior or concurrent malignancy whose natural history or treatment does not have the potential to interfere with the safety or efficacy assessment of the trial are eligible.
NOTE: consultation with the Overall PI is highly recommended if enrollment of a patient with a prior or concurrent malignancy will be pursued.

3.1.16 Patients must be undergoing surgery that is clinically indicated as determined by their care providers. Patients must be eligible for surgical resection with the expectation that the surgeon is able to resect at least 400mg of tumor with low risk of inducing neurological injury.

3.1.17 Female subjects of childbearing potential must have a negative urine or serum pregnancy within 72 hours prior to registration. If the urine test is positive or cannot be confirmed as negative, a serum pregnancy test will be required. Women are considered post-menopausal and not of child bearing potential if they have had 12 months of natural (spontaneous) amenorrhea with an appropriate clinical profile (e.g., age appropriate, history of vasomotor symptoms) or six months of spontaneous amenorrhea with serum FSH levels > 40 mIU/mL and estradiol < 20 pg/mL or have had surgical bilateral oophorectomy (with or without hysterectomy) at least six weeks ago. In the case of oophorectomy alone, only when the reproductive status of the woman has been confirmed by follow up hormone level assessment is she considered not of child bearing potential.

3.1.18 Women of child-bearing potential (WOCBP), defined as all women physiologically capable of becoming pregnant, must agree to use highly effective contraception during study treatment and for 120 days after study discontinuation. Highly effective contraception is defined as either:

- i. True Abstinence: When this is in line with the preferred and usual lifestyle of the subject. Periodic abstinence (e.g., calendar, ovulation, symptothermal, post-ovulation methods) and withdrawal are not acceptable methods of contraception.
- ii. Sterilization: Surgical bilateral oophorectomy (with or without hysterectomy) or tubal ligation at least six weeks ago. In case of oophorectomy alone, only when the reproductive status of the woman has been confirmed by follow up hormone level assessment (as described in item 3.1.16 above).
- iii. Male Partner Sterilization (with the appropriate post-vasectomy documentation of the absence of sperm in the ejaculate). For female subjects on the study, the vasectomized male partner must be the sole partner for that participant.
- iv. Use of a combination of any two of the following:
 - a. Placement of an intrauterine device (IUD) or intrauterine system (IUS)
 - b. Barrier methods of contraception: Condom or Occlusive cap (diaphragm or cervical/vault caps) with spermicidal foam/gel/film/cream/vaginal suppository
 - c. Appropriate hormonal contraceptives (including any registered and marketed contraceptive agent that contains an estrogen and/or a progestational agent – including oral, subcutaneous, intrauterine, or intramuscular agents)

3.1.19 Male subjects must agree to use adequate method of contraception starting with the first dose of study therapy through 120 days after the last dose of therapy.

3.2 Eligibility Exclusion Criteria

The subject must be excluded from participating in the trial if the subject:

3.2.1 Current or planned participation in a study of an investigational agent or using an investigational device.

3.2.2 Has a diagnosis of immunodeficiency.

3.2.3 Has tumor primarily localized to the brainstem or spinal cord.

3.2.4 Has presence of diffuse leptomeningeal disease or extracranial disease.

3.2.5 Has received systemic immunosuppressive treatments, aside from systemic corticosteroids (such as methotrexate, chloroquine, azathioprine, etc) within six months of registration.

3.2.6 Has received anti-angiogenic or anti-VEGF targeted agents (e.g. bevacizumab, cediranib, aflibercept, vandetanib, XL-184, sunitinib, etc).

3.2.7 Requires treatment with high dose systemic corticosteroids defined as dexamethasone > 4 mg/day or bioequivalent for at least 3 consecutive days within 2 weeks of registration.

3.2.8 Has received prior interstitial brachytherapy, implanted chemotherapy, stereotactic radiosurgery or therapeutics delivered by local injection or convection enhanced delivery.

3.2.9 Has history of known coagulopathy that increases risk of bleeding or a history of clinically significant hemorrhage within 12 months of registration.

3.2.10 Has a known history of active TB (Bacillus Tuberculosis).

3.2.11 Has gastrointestinal bleeding or any other hemorrhage/bleeding event CTCAE Grade > 3 within 6 months of registration.

3.2.12 Has active autoimmune disease that has required systemic treatment in the past 2 years (i.e. with use of disease modifying agents, corticosteroids or immunosuppressive drugs). Replacement therapy (eg., thyroxine, insulin, or physiologic corticosteroid replacement therapy for adrenal or pituitary insufficiency, etc.) is not considered a form of systemic treatment.

3.2.13 Has known history of, or any evidence of active non-infectious pneumonitis.

3.2.14 Has an active infection requiring systemic therapy.

3.2.15 Has a history or current evidence of any condition, therapy, or laboratory abnormality that might confound the results of the trial, interfere with the subject's participation for the full duration of the trial, or is not in the best interest of the subject to participate, in the opinion of the treating investigator. Examples include but are not limited to symptomatic congestive heart failure, unstable angina pectoris, cardiac arrhythmia or psychiatric illness/social situations that would limit compliance with study requirements.

3.2.16 Has known psychiatric or substance abuse disorders that would interfere with cooperation with the requirements of the trial.

3.2.17 Has received prior therapy with an anti-PD-1, anti-PD-L1, anti-PD-L2, anti-CD137, or anti-Cytotoxic T-lymphocyte-associated antigen-4 (CTLA-4) antibody (including ipilimumab or any other antibody or drug specifically targeting T-cell co-stimulation or checkpoint pathways).

3.2.18 Has a known history of Human Immunodeficiency Virus (HIV) (HIV 1/2 antibodies).

3.2.19 Has known active Hepatitis B (e.g., HBsAg reactive) or Hepatitis C (e.g., HCV RNA [qualitative] is detected).

3.2.20 Has received a live vaccine within 30 days prior to registration.

3.2.21 Has a known hypersensitivity to any of the study therapy products.

3.3 Inclusion of Women and Minorities

Both men and women of all races and ethnic groups are eligible for this trial.

4. REGISTRATION PROCEDURES

All sites should email the Study Coordinator email to [contact] to verify slot availability.

4.1 General Guidelines for DF/HCC Institutions

Institutions will register eligible participants in the Clinical Trial Management System (CTMS) OnCore. Registrations must occur prior to the initiation of protocol-specific therapy or intervention. Any participant not registered to the protocol before protocol therapy begins will be considered ineligible and registration will be denied.

An investigator will confirm eligibility criteria and a member of the study team will complete the ODQ protocol-specific eligibility checklist.

Following registration, participants may begin protocol therapy and/or intervention. Issues that would cause treatment delays should be discussed with the Overall Principal Investigator (PI). If

a participant does not receive protocol therapy following registration, the participant's participant must be taken off-study in the CTMS (OnCore) with an appropriate date and reason entered.

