1. OBJECTIVES

1.1 Study Design

This is a multicenter, randomized, open-label, pilot surgical trial of pembrolizumab (MK-3475) among bevacizumab naive, surgically resectable recurrent glioblastoma patients. Please see Figure 1 for Schema.

Group A: pembrolizumab (MK-3475) at 200 mg IV within 14 ± 5 days prior to surgery. Post-surgery subjects will receive pembrolizumab at 200mg IV every three weeks.

Group B: no pembrolizumab (MK-3475) prior to surgery. Post-surgery subjects will receive pembrolizumab at 200mg IV every three weeks.

After recovering from surgery, subjects will be evaluated every 6 weeks with radiographic imaging to assess response to treatment. The Response Assessment in Neuro-Oncology (RANO) criteria will be used as the efficacy endpoint of response rate. A modified RANO (iRANO)¹¹¹ (as described in Section 10.0) will be used to evaluate response and progression in an exploratory fashion due to the tumor response patterns seen with pembrolizumab treatment (e.g., tumor flare). Adverse events will be monitored throughout the trial and graded in severity according to the guidelines outlined in the NCI Common Terminology Criteria for Adverse Events (CTCAE) version 5.0. Treatment with study therapy will continue until documented disease progression, unacceptable adverse event(s), intercurrent illness that prevents further administration of treatment, investigator's decision to withdraw the subject, subject withdraws consent, pregnancy of the subject, noncompliance with trial treatment or procedure requirements, or administrative reasons. After the end of treatment, each subject will be followed for 30 days for adverse event monitoring and 90 days for serious adverse event reporting. Subjects who discontinue treatment for reasons other than disease progression will have post-treatment follow-up of disease status until disease progression, initiation of a non-study cancer treatment, withdrawing consent, or becoming lost to follow -up. All subjects will be followed by telephone contact or medical record review for overall survival until death, withdrawal of consent or the end of the study, whichever comes first.

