5. TREATMENT PLAN

This is a pilot surgical trial to evaluate early immunologic pharmacodynamic parameters for the PD-1 checkpoint inhibitor, pembrolizumab (MK-3475), in patients with surgically accessible recurrent/progressive glioblastoma. The principle goal of this study is to understand, in surgically resectable recurrent/progressive GBM, if neoadjuvant pembrolizumab elicits a systemic immunologic response, a tumoral immunologic response and toxicity and if that response can be correlated with other non-invasive measures of pembrolizumab bioactivity (tumor, blood, imaging, and clinical outcomes). The study includes 2 stages, in the first stage (**Stage 1**), for optimal understanding of the effect of the drug on tumor tissue patients will be randomized in to Group A or Group B. In the second stage (**Stage 2**), additional patients will be enrolled to an expansion arm of Group A only to specifically study the effect of the drug on cell cycle/cancer proliferation related genetic signature.

Stage 1:

Groups A and B: Patients will be randomly assigned to either group A or B with a 1:1 randomization ratio prior to surgery. Patients in all groups will receive the study drug pembrolizumab after tumor resection. Only Group A will receive a single infusion of pembrolizumab of 200mg 14± 5 days prior to surgery (when scheduling, please keep in mind that the two pre-surgical plasma samples should be drawn greater than 10 days apart - see Table 6 for full details). Group B will not receive study drug prior to surgery. **This randomization scheme should not negatively impact study accrual and will provide an invaluable control cohort for PD evaluations.**

Group A: Neoadjuvant/adjuvant evaluation: Fifteen eligible patients will receive a single infusion of pembrolizumab of 200mg 14± 5 days prior to scheduled surgical resection for

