Group B: adjuvant evaluation: Fifteen eligible patients will not receive study drug prior to scheduled surgical resection for recurrent/progressive glioblastoma. The two required pre-surgical plasma samples should be drawn greater than 10 days apart - see Table 6 for full details). Tumor samples will be obtained at time of surgery. The tissue from this surgery (fresh, frozen and FFPE) and the archived tissue from the most recent surgery prior to registration revealing glioblastoma (FFPE) will be processed so as to best achieve the primary, secondary and exploratory PD objectives. After recovery from surgery (once participant has recovered from surgery, but no more than 35 days following surgery), patients will begin Q 3 week pembrolizumab at 200mg IV until tumor progression or adverse event requiring discontinuation of study drug. Blood samples will be obtained as pharmacodynamic markers throughout the study. Dose decreases and symptomatic management will occur based upon preset adverse event determination. DLTs will not be determined. The toxicity evaluation period will begin with registration and extend to 30 days after last treatment day. Patients will be followed for MRI changes, clinical exam and steroid doses from the registration period and extend to the second progression. After second progression, patients will be followed every 3 months for vital status until death.

Stage 2:

Group A expansion only: For this stage of the study, 25 additional patients will be enrolled to Group A only with a goal of 20 evaluable patients.

Expansion of Group A: Neoadjuvant/adjuvant evaluation: An additional 20-25 patients will receive a single infusion of pembrolizumab of 200mg 14± 5 days prior to scheduled surgical resection for recurrent/progressive glioblastoma (when scheduling, please keep in mind that the two pre-surgical plasma samples should be drawn greater than 10 days apart - see Table 6 for full details). Tumor samples will be obtained at time of surgery. The tissue from this surgery (fresh, frozen and FFPE) and the archived tissue from the archived tissue from the most recent surgery prior to registration revealing glioblastoma (FFPE) will be processed so as to best achieve the primary, secondary and exploratory PD objectives. After recovery from surgery (once participant has recovered from surgery, but no more than 35 days following surgery), patients will resume Q 3 week pembrolizumab at 200mg IV until tumor progression or adverse

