5.11 Long-Term Follow-Up and Study Completion

After documented disease progression each subject will be followed by telephone or medical record review for overall survival until they meet criteria for removal from study as detailed below.

Participants will be removed from study when any of the following criteria apply:

- Lost to follow-up
- Withdrawal of consent
- Death

The reason for taking a participant off study, and the date the participant was removed, must be documented in the case report form (CRF).

When a participant is removed from protocol therapy and/or is off of the study, the relevant Off-Treatment/Off-Study information will be updated in OnCore.

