12.2.5 Analysis Population

12.2.5.1 Efficacy Analysis Populations

The Full Analysis Set (FAS) population will serve as the primary population for the analysis of efficacy data in this study. The FAS population consists of all subjects within each cohort who have received at least one dose of study treatment.

Two supportive analyses of the primary and selected secondary efficacy endpoints will be conducted. The first supportive analysis will be conducted in the FAS-2 population, defined as all subjects who meet the FAS population definition and have a post baseline scan OR discontinue the trial due to progressive disease/drug related AE. The second analysis will be conducted using the intention to treat (ITT) population, defined as all randomized subjects.

Subjects will be included in the cohort to which they are randomized for the analysis of efficacy data.

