3.7 DF/HCC Multi-Center Protocol Registration Policy

Eligible participants will be registered onto trial with the DF/HCC Office of Data Quality (ODQ) central registration system (by a Coordinating Center specialist, if participant is at a non-DF/HCC site). Registration must occur prior to the initiation of therapy. Any participant not registered to the protocol before treatment begins will be considered ineligible and registration will be denied.

A qualified member of the study team will confirm eligibility criteria and complete the protocol-specific eligibility checklist.

Issues that would cause treatment delays should be discussed with the Principal Investigator. If a participant does not receive protocol therapy following registration, the participant's protocol status must be changed. Notify the ODQ Registrar (a Coordinating Center specialist, if participant is at a non-DF/HCC site) of participant status changes as soon as possible.

In order to register a participant onto study, the following must be done:

- Obtain written informed consent from the participant prior to the performance of any study related procedures or assessments.
- Complete the protocol-specific eligibility checklist using the eligibility assessment documented in the participant's medical/research record. **To be eligible for registration to the study, the participant must meet each inclusion and exclusion criteria listed on the eligibility checklist.**

Reminder: Confirm eligibility for ancillary studies at the same time as eligibility for the treatment study. Registration to both treatment and ancillary studies will not be completed if eligibility requirements are not met for all studies.

Treatment may not begin without confirmation from the Coordinating Center that the participant has been registered.

Randomization can only occur during ODQ's normal business hours, Monday through Friday from 8:00 AM to 5:00 PM Eastern Standard Time.

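### Section 4.1 takes registered but untreated participants off study, contrary to 5.11 and 1.1; in Stage 1 the lost follow-up would fall mainly on Group B

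*Combined protocol and SAP*

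**What the plan says.** Four places in the combined protocol and SAP govern a participant who is registered but never dosed.

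- Section 4.1 (DF/HCC institutions): if "a participant does not receive protocol therapy following registration, the participant's participant must be taken off-study in the CTMS (OnCore"), with a date and a reason entered.
- Appendix B 3.7, to which sections 4.3 and 4.4 send other sites: "If a participant does not receive protocol therapy following registration, the participant's protocol status must be changed". It does not say off study.
- Section 5.11: "Participants will be removed from study when any of the following criteria apply". The list is loss to follow-up, withdrawal of consent and death.
- Section 1.1, with closure of the trial as the last stopping point: "All subjects will be followed by telephone contact or medical record review for overall survival until death, withdrawal of consent or the end of the" […]. The treatment plan in section 5 adds, for each group: "After second progression, patients will be followed every 3 months for vital status until death".

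The timing of the first dose differs by group. In Stage 1, "Patients will be randomly assigned to either group A or B with a 1:1 randomization ratio prior to surgery", and "Only Group A will receive a single infusion of pembrolizumab of 200mg 14± 5 days prior to surgery". Group B first receives pembrolizumab once recovered from surgery, at most 35 days after it.

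Section 12.2.5.1 makes the FAS (at least one dose) the primary efficacy population. It adds a supportive analysis in the "intention to treat (ITT) population, defined as all randomized subjects", limited to the primary and selected secondary efficacy endpoints. Section 12.2.6.1 censors subjects without efficacy or survival data at Day 1. Section 12.2.6.3 plans log-rank comparisons of PFS, second PFS and OS between the groups and names no population for them.

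**The concern.** A site cannot follow 4.1 and also follow 5.11 and 1.1. The conflict matters more here than in a trial where both arms start treatment together. Randomisation comes before surgery, one arm is dosed before the operation and the other only after recovery from it. The same perioperative setback therefore leaves a Group A patient on study, already dosed, and makes a Group B patient someone who never received protocol therapy.

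Those Group B patients are likely to be early failures. If their follow-up stops, the missing data depend on both group and prognosis, and Day 1 censoring removes them from the risk set before any event is counted. At stake are the exploratory comparison of Group A with Group B for PFS and OS, if run on all randomised patients, and the supportive ITT analysis of PFS6, if PFS6 is one of the selected endpoints.

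**Working it through.** **1. Is surgery protocol therapy?** If it were, an operated Group B patient would escape the rule. The text points the other way. Table 2 in section 5.1 lists only pembrolizumab as trial treatment, inclusion criterion 3.1.16 requires the operation to be clinically indicated, and 4.1 itself names therapy and intervention separately. Sections 5.9 and 5.11 also refer to off-treatment alongside off-study information in OnCore, so a milder status was available and 4.1 did not use it.

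**2. Time at risk of being registered but undosed (Stage 1).**
- Group A: registration to the pre-surgical dose. That dose falls 14 − 5 = 9 to 14 + 5 = 19 days before surgery, so perioperative events come after it.
- Group B: registration, a pre-surgical interval of more than 10 days (two plasma samples must be that far apart), the operation, then recovery of up to 35 days. From first sample to first dose this can exceed 10 + 35 = 45 days and includes the whole perioperative period.

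The direction follows from the schedule. The size does not, because the documents give no count of undosed patients.

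**3. Effect on a survival estimate (assumed numbers).** Take 15 Group B patients, 9 truly alive at 6 months, with k of the 6 early deaths occurring after removal under 4.1. With Day 1 censoring and no other censoring, the Kaplan-Meier estimate is 9/(15 − k):
- k = 0: 9/15 = 60.0%
- k = 1: 9/14 = 64.3%
- k = 2: 9/13 = 69.2%

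**4. Effect on the log-rank comparison (assumed model).** 15 per arm, exponential survival, true hazard ratio 0.39 (the interim value in section 1.1), cut-off at 18 months, two-sided 0.05, 4,000 simulated trials per cell. The k earliest Group B deaths are censored at Day 1, which is the worst case. Entries are the chance of a significant result favouring Group A, with full follow-up → after the loss.

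| Group B median | k = 1 | k = 2 | k = 3 |
|---|---|---|---|
| 6 months | 58% → 52% | 58% → 45% | 57% → 36% |
| 9 months | 49% → 42% | 50% → 36% | 49% → 29% |
| 12 months | 42% → 34% | 42% → 28% | 43% → 21% |

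**5. Direction.** Between groups, the loss makes Group B look better and works against Group A. In PFS6, which pools both groups against historical controls, it would raise the pooled estimate.

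**6. What is not touched.** The plan gives no figure on this point. The nearest one, 85% power for TIL density with 15 per group, reproduces at 84.8% (one-sided t-test, standardised difference 0.5/0.5 = 1). It is unaffected by the loss of follow-up, because the tissue is taken at surgery, before an operated Group B patient could be removed under 4.1.

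**The case against.** The case for leaving this alone has real content.

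- A reader might infer that the rule defeats a planned ITT analysis of PFS and OS. The documents do not support that. ITT covers the primary and selected secondary endpoints; PFS6 is the only secondary efficacy endpoint, while time-to-event PFS and OS are exploratory with no population named.
- A reader might infer that the rule is trial-wide. The explicit off-study wording is for DF/HCC institutions, and no split of patients by site is given.
- It is tempting to say that only Group B is affected. Group A patients can also miss their first dose, and section 3 foresees toxicity management between registration and the start of treatment. Mainly Group B, in Stage 1, is as far as the text goes.
- It is tempting to say that the outcome is lost for good. For survival that is too strong, since record review is already a protocol method and a death before removal could be entered as the reason. Progression status is harder to recover.
- The FAS drops undosed patients whatever 4.1 says, so rewording 4.1 does not change the primary efficacy analysis.
- Stage 2 enrols Group A only. Section 1.1 reports 35 patients enrolled by September 2017 against about 30 evaluable planned for Stage 1, so Group B accrual appears complete and few future Group B patients would benefit.

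All of these stand as limits. None removes the contradiction between 4.1 and sections 5.11 and 1.1, or the imbalance in who is exposed to it. That 4.1 could be read as a mere system entry is a reason to clarify it.

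**Conclusion.** The concern holds in a limited form. Section 4.1 conflicts with 5.11 and 1.1, and Appendix B 3.7 words the same situation differently. In Stage 1 the resulting loss of follow-up would fall mainly on Group B's perioperative failures and would flatter Group B in any all-randomised analysis.

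The size is unknown and may be small. The 60% to 69% shift and the simulated loss of significance rest on assumed counts, exponential survival and worst-case removal of the earliest deaths. They also assume that sites act on 4.1 by stopping follow-up, and that the Day 1 rule, stated alongside the PFS analysis, is applied to OS too.

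A reader might infer that this rule produced the interim survival advantage reported for Group A (hazard ratio 0.39, P = 0.04). Nothing in the documents supports that. They do not say that any patient was removed under 4.1, and the expected bias runs the other way.

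**What to change.** 1. Amend 4.1 and Appendix B 3.7 to the same wording: a registered or randomised participant who receives no pembrolizumab is recorded as off treatment, with date and reason, and stays in disease-status and 3-monthly survival follow-up until a criterion in 5.11 is met. Apply it to both groups and both stages.
2. Trace survival by record review, within consent, for any Stage 1 patient already removed under this rule, and report how many there were in each group.
3. In 12.2.6.3, state that the exploratory comparison of Group A with Group B for PFS and OS will be reported in all randomised Stage 1 patients as well as in the FAS. Without this step, the recovered follow-up has no specified use in that comparison.

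The cost is a short amendment to three sections, and telephone or record-review follow-up for what is probably a few patients, by a procedure the protocol already uses. No change to treatment, sample size or the primary endpoints is involved.
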